3. INVESTIGATION PLAN

3.1. Overall Study Design and Plan Description

An overview of study design is shown in [Figure 1](#). This is a multicentre, open-label, controlled Phase 3 study in which adults requiring hospital admission and O₂ supplementation for management of moderate COVID-19 infection will be randomised in 1:1:1 to:

- Plitidepsin 1.5 mg arm: Patients will receive plitidepsin 1.5 mg/day intravenous (IV) in addition to dexamethasone on days 1 to 3 ([See Section 5. Study treatments](#)).
- Plitidepsin 2.5 mg arm: Patients will receive plitidepsin 2.5 mg/day IV in addition to dexamethasone on days 1 to 3 ([See Section 5. Study treatments](#)).
- Control arm: Patients will receive dexamethasone IV on Days 1 to 3. Additionally, in accordance with local treatment guidelines, patients in this group may receive a regulatory-approved antiviral treatment ([See Section 5. Study treatments](#)).

Randomisation will be stratified for 3 factors:

- a) Geographical Region (Europe *versus* Rest of the World);
- b) Charlson Comorbidity Index (0-1 *versus* >1) ([Appendix 11 – Age-adjusted Charlson Index](#)); and
- c) Barthel Index (≥ 90 *versus* <90) ([Appendix 7 - Barthel Index for Functional Assessment](#)).

[figure not shown]
From treatment initiation on Day 1, patients will be followed in the hospital for at least 4 days and then through Day 31 (± 3 days) or resolution/stabilisation of treatment-related adverse events, treatment-emergent adverse events of special interest, and SAEs. Patients discharged from the hospital prior to Day 8 will return to an out-patient clinic for assessments on Days 8 (± 1 day) and 31 (± 3 days). On Day 15 (± 1 day), patients will be followed up in remote or on-site visit ([Appendix 5 – Schedule of Assessments](#)).

An Independent Data Monitoring Committee (IDMC) will oversee study conduct (safety and primary endpoint), including analysis of summary safety data as per the trial requirements.

The study is expected to randomise approximately 609 patients (203 in each arm) over a period of 20 months.

Patients will be considered to be on study from the signature of the informed consent form (ICF) until the end of the follow-up period, that is, completion of the protocol-specified follow-up visit on Day 31 (± 3 days) or until resolution/stabilisation of treatment-related AEs, treatment-emergent adverse events of special interest, and SAEs that occurred through Day 31, whichever is longer.

Figure 1. Schema of the Study

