7.2.1. Adverse Events

Adverse event definitions and assignment of severity and causality are detailed in [Appendix 1](#). All adverse events (AE) and adverse reactions (ARs), based on clinical signs and symptoms and laboratory measurements, will be measured daily until Day 31 (± 3 days), except treatment-related adverse events, treatment-emergent adverse events of special interest, and SAEs that will be measured daily until resolution or stabilisation to at least Grade 1, or to an acceptable level according to the investigator and the sponsor of his/her designated representative.

Adverse events will be elicited from the patient (or, when appropriate, from a caregiver, surrogate, or the patient's legally authorised representative) by the study site staff using a non-leading question such as "How are you feeling today?" or "Have you had any health concerns since your last visit?"

The investigator and any designees are responsible for detecting, documenting, and reporting events that meet the definition of an AE or SAE and remain responsible for following up AEs that are serious, considered related to the study treatment or the study, or that caused the patient to discontinue the study treatment (see [Section 4.4.2](#)).

Clinical Signs and Symptoms: AEs, including worsening of baseline signs and symptoms of disease observed by the investigator (preferably by the same physician for a same patient) or reported by patients to study nurses will be recorded and graded according to NCI-CTCAE version 5.0, accessible via internet

(http://ctep.cancer.gov/protocolDevelopment/electronic_applications/docs/CTCAE_v5_Quick_Reference_8.5x11.pdf). All events, including those considered not related to the study drugs, must be reported in the eCRF.

The following AEs will be considered and monitored as AEs of special interest: musculoskeletal disorders, CPK increases, and rhabdomyolysis; hypersensitivity reactions, cardiac events and transaminase elevations, and hepatobiliary disorders.

Laboratory Abnormalities: Laboratory abnormalities will be recorded and graded according to NCI-CTCAE version 5.0, accessible via internet (http://ctep.cancer.gov/protocolDevelopment/electronic_applications/docs/CTCAE_v5_Quick_Reference_8.5x11.pdf). Laboratory abnormalities that are of clinical significance will be recorded in Adverse Event eCRF.

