Clinically significant new findings seen on any ECGs taken after screening should be recorded as AEs.

Additionally, a dedicated QTc substudy will be performed in a subset of approximately 50 patients with ECGs collected over Days 1 to 3 using Holter monitors to assess treatment impact on QTc prolongation. See [Appendix 8](#) for objectives and respective endpoints planned for the QTc substudy. The substudy patients will have blood sampling for pharmacokinetic assessments over Days 1 to 4.

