- To explore plitidepsin pharmacokinetics in patients with COVID-19

OVERALL SUBSTUDY DESIGN

This QT substudy is to be performed in a subset of sites of the multicentre, randomised, Phase 3 clinical trial APL-D-003-20 conducted in patients with COVID-19.

The selection of sites will be made based on the site's feasibility to accomplish the QT evaluation study procedures.

Patients will be enrolled, as needed, to ensure that there are 50 evaluable patients in more than 80% of the scheduled ECG timepoints.

A continuous digital ECG recorder (Holter) will be provided by a third-party central ECG laboratory after the site has completed the site qualification requirements. Once the site has finished participation in the QT evaluation study, a recall notification will be sent to the investigator to return the equipment.

Study nurse and site personnel in charge of the QT substudy procedures will be trained and certified by means of 2 on-line courses about patient's preparation and use of the ECG equipment.

After completing all other baseline assessments on Day 1, a 12-lead continuous ECG recorder will be set in place. Patients will stay at the study site on Days 1 to 4 until completion of the pharmacokinetic (PK) blood sample collection scheduled at 24 hours after end of Day 3 infusion.

On Days 1, 2, and 3, administered the prophylactic medications to patients should be ideally completed 20 to 30 minutes before the start of infusion and, exceptionally, up to 2 h pre-infusion of plitidepsin.

Details on the timing of the treatment and assessments are given in the substudy Schedule of Assessments and Procedures (see below).

PATIENT DEFINITION

Substudy Population

Patients will be enrolled in the substudy as needed to ensure that approximately 50 patients have completed all required assessments.

Patient Eligibility

Inclusion Criteria

To be enrolled in the substudy, patients must satisfy the following criteria at screening for the main study:

1. Patient included in the clinical study APL-D-003-20 and randomised to the experimental arm (plitidepsin).
2. Patient with voluntarily signed and dated informed consent to participate in the QT substudy.
3. A 12-lead ECG consistent with normal cardiac conduction and function, showing:
 - Sinus rhythm.
 - Heart rate between 45 and 100 beats per minute.
 - QTcF \leq 450 msec for males or \leq 470 msec for females.
 - QRS interval $<$ 110 msec.
 - PR interval $<$ 200 msec.

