Once all samples from a patient have been collected, they should be shipped to the designated laboratory as soon as possible, ideally the next shipping day. If the same centre has samples from several patients, samples can be sent in the same shipment. However, the time span between the moment the last PK sample for a patient has been

collected and the shipment of all samples from this patient to the laboratory should not exceed 2 months.

A manual of full instructions for sample extraction, labelling, storage, and shipment will be provided as a separate document.

ECG Evaluations

12-lead ECG Acquisition

The ECGs will be obtained digitally using a Mortara Instrument (Milwaukee, WI, USA) H-12+ECG continuous 12-lead digital recorder, which will obtain ECGs on Day 1 through Day 3. The ECGs will be stored continuously on a flash card and will not be available for review until the card is received by the emergency response team (ERT) and analysed. The patient's unique identification number and demographic information will be recorded for each card.

Patients will wear the continuous ECG recorder (Holter) from Days 1 to 3 (24 hours after end of infusion of Day 2). This ECG recorder will be provided by ERT after the study site has registered online at ERT's MYSTUDY PORTAL™. Registration details will be provided to the site coordinator at each participating site.

The ECG recorder will be set in place once all safety assessments scheduled for the main study (i.e., vital signs, blood sample extraction for laboratory tests, and ECG) have been conducted.

In this QT substudy, using pretreatment ECGs as the baseline and individual heart rate QT-correction, the Holter will be started, ideally, no less than 3 hours prior to the start of infusion of Day 1 through approximately 24 hours after the end of infusion of Day 2 (until the end of infusion on Day 3).

ECG Analysis Methods

All digital continuous ECG recordings will be sent to a third-party, central ECG laboratory ERT. The ECG readers will be blinded to patient identifiers and visit. All ECGs for a given patient will be analysed by the same reader. Quality Assurance reports for inter- and intra-observer variability will be produced by the central ECG laboratory and provided to the sponsor.

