For the triplicate ECGs collected at each timepoint, the average of the 3 measurements for each ECG parameter will be considered for all listing and statistical analyses described below.

Investigators are not expected to evaluate or otherwise assess the ECGs unless alerted by the central ECG laboratory to the possibility of a clinically relevant reading.

QT Correction Methods

The QT will be corrected for heart rate using the following methods:

- QTcF³
- Estimation of the exponent at an individual level (QTcI)⁹

The most appropriate method, based on the lack of statistical significance of the slope between QTc and heart rate, will be used for the concentration-QTc analysis.

Endpoint definition

In principle, for each patient and each postdose timepoint on Days 1 to 3, baseline QTc intervals will be the mean of the predose 1 and predose 2 QTc values for that patient on Day 1.

If the mean predose 2 QTc value of all evaluable patients is ≥ 10 msec longer than of the mean predose 1 QTc value, an effect of prophylactic medication on QTc cannot be ruled out; therefore, individual predose 2 QTc values will be considered as the baseline values.

The change from baseline (Δ QTc) will be calculated using the corresponding baseline QTc values. Specifically:

- Δ QTc at time t: Difference in QTc between scheduled timepoint t and baseline.

The primary endpoint will be Δ QTc at each scheduled timepoint.

STATISTICAL METHODS

Sample Size

Assuming that the intrasubject standard deviation for change from baseline in QTc (Δ QTc) is 30 msec and that the true difference between means is 5 msec, a sample size of at least 25 evaluable patients in more than 80% of the scheduled ECG timepoints t is planned to have 80% power to show that the upper limit of the 2-sided 90% confidence interval (CI; 1-sided upper 95% CI) for mean Δ QTc at each ECG timepoint t is < 20 msec.

Primary Analysis

“By Timepoint” Analysis

The primary objective of this QT evaluation study is to measure the potential effect of plitidepsin on QTc. The primary comparison of interest is Δ QTc at each ECG timepoint t. A noninferiority criterion of 20 msec will be used to establish that postbaseline QTc is noninferior to baseline.

An analysis of variance model (ANOVA) with mixed effects will be fitted, with Δ QTc data as the dependent variable and ECG timepoint t as the fixed effects, and patient as random effect.

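### Only plitidepsin patients enter the Holter QTc substudy, and reportable Holter findings are not separated in the main safety tables, so the descriptive cardiac AE comparison with control is open to detection bias

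*Protocol*

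**What the plan says.** **Who is monitored.** Appendix 8 (Inclusion Criteria) limits the substudy to a "Patient included in the clinical study APL-D-003-20 and randomised to the experimental arm (plitidepsin"). On size it says: "Patients will be enrolled in the substudy as needed to ensure that approximately 50 patients have completed all required assessments". For the main trial, section 3.1 says: "The study is expected to randomise approximately 609 patients (203 in each arm) over a period of 20 months".

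**How they are monitored.** Appendix 8 says: "Patients will wear the continuous ECG recorder (Holter) from Days 1 to 3 (24 hours after end of infusion of Day 2"). It adds: "All digital continuous ECG recordings will be sent to a third-party, central ECG laboratory ERT". Triplicate ECGs are extracted at four post-dose timepoints on each of Days 1 and 2. A cardiologist verifies intervals and reviews morphology. New atrial fibrillation or flutter, higher-degree AV block, bundle branch block and infarction are reported. Every other patient has the scheduled triplicate ECGs at screening and on Days 1, 3 and 31 (Appendix 5), plus ECGs prompted by an event.

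**How a Holter finding can become an adverse event.** Investigators do not assess the substudy ECGs "unless alerted by the central ECG laboratory to the possibility of a clinically relevant reading". Section 7.2.5 then applies: "Clinically significant new findings seen on any ECGs taken after screening should be recorded as AEs". The paragraph after that sentence introduces the Holter substudy.

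**Where the event is counted.** Section 7.2.1 lists as events of special interest, among others, "hypersensitivity reactions, cardiac events and transaminase elevations, and hepatobiliary disorders". Their frequency is an endpoint (section 2.2) under an objective to compare safety with control (section 2.1). Section 8.7 summarises treatment-emergent events by treatment group and lists those of special interest. It tabulates QTcF above 500 msec and changes above 60 msec without saying which ECGs count. It has no rule for events found only through the substudy.

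**The concern.** A between-arm comparison of event frequency is clean only if each arm is searched equally hard. Here one plitidepsin patient in eight is searched much harder than any control patient, on the days of dosing, and for the type of event the trial treats as of special interest. Asymptomatic rhythm or conduction findings that a control patient might also have had would go unseen in that arm.

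At stake is how a cardiac excess on plitidepsin is read. Without a record of how each event was found, detection could pass for a drug effect, and a real drug effect could be dismissed as a Holter artefact. The dose comparison is exposed too, because Appendix 8 does not fix how the 50 patients divide between 1.5 mg and 2.5 mg. The trial is also open-label, so the investigator who judges clinical significance knows the arm.

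**Working it through.** **1. The substudy's own sample size.** Appendix 8 assumes an SD of 30 msec, a true mean change of 5 msec, a margin of 20 msec, a one-sided 5% level and 80% power.

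n = [30 × (1.645 + 0.842) / (20 − 5)]² = 24.7, rounded up to 25.

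This reproduces the stated minimum of 25. It is a single-group calculation and fits the substudy's change-from-baseline objective. The absence of controls is therefore a coherent choice for that objective.

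**2. Share of patients with extra monitoring.** Plitidepsin patients: 203 + 203 = 406.
- Pooled plitidepsin: 50/406 = 12.3%.
- Control: 0/203 = 0%.
- One dose arm, if it held all 50: 50/203 = 24.6%.

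**3. ECG reading density.** Scheduled on-treatment ECGs common to all arms: 2 (Days 1 and 3). Post-dose Holter sets: 4 × 2 = 8.
- Plitidepsin: (406 × 2 + 50 × 8)/406 = 1,212/406 = 2.99 per patient.
- Control: 2.00 per patient.
- Plitidepsin readings with no control counterpart: 400/1,212 = 33%, or 400/1,618 = 25% if Day 31 is counted.

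These are counts of readings, not of reportable events. They show unequal search effort and do not measure the bias.

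**4. Possible effect on event rates.** Let q be the share of Holter wearers with a reportable finding that would otherwise have been missed. The protocol gives no value, so the range is an assumption. The rise in the rate is 50q/406 for the pooled arms, or 50q/203 if all 50 are in one arm. The last column assumes a true rate of 5% in every arm and no drug effect.

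| q | Extra patients | Pooled rise (points) | One-arm rise (points) | Pooled ratio to control |
|---|---|---|---|---|
| 2% | 1 | 0.25 | 0.5 | 1.05 |
| 5% | 2.5 | 0.6 | 1.2 | 1.12 |
| 10% | 5 | 1.2 | 2.5 | 1.25 |
| 20% | 10 | 2.5 | 4.9 | 1.49 |

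**5. A second parameterisation.** Suppose the shared ECGs find an event in r = 2% to 5% of patients and Holter wearers show one in h = 5% to 10% (also assumptions). With w = 50/406 and no drug effect, the ratio is [(1 − w)r + wh]/r.
- r = 5%, h = 5%: 1.00.
- r = 5%, h = 10%: (0.0438 + 0.0123)/0.05 = 1.12.
- r = 2%, h = 5%: (0.0175 + 0.0062)/0.02 = 1.18.
- r = 2%, h = 10%: (0.0175 + 0.0123)/0.02 = 1.49.

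The range is 1.00 to 1.49. It includes no bias at all, which occurs when the Holter finds nothing reportable beyond the shared ECGs.

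**The case against.** A reader might infer that every Holter finding becomes an adverse event and that the comparison is therefore certain to be biased. The protocol does not support that. A finding must first prompt a central-laboratory alert and then be judged new and clinically significant. Appendix 1 likewise limits reporting of abnormal tests to results that are symptomatic, change management, meet a seriousness criterion or are clinically relevant. QTc outliers and morphology changes also have their own substudy tables.

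Other points weigh against a large effect:
- The substudy selects a low-risk group: age 65 or under, sinus rhythm, normal conduction, and no recent significant coronary disease.
- Monitoring lasts two to three days.
- The cardiac comparison is descriptive. No test, margin or threshold rests on it, and the numeric safety trigger in section 3.1.1 uses deaths and Grade 3 or higher SAEs.
- Sensitivity tables for safety data often sit in the SAP, which is not shown. Substudy patients keep their main-trial number, so a summary without them could be produced at any time.
- Taking Holter-found events out of the main comparison could hide a true drug-induced arrhythmia.

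Most of this stands, and it limits the size and severity. It does not close the gap. The recording rule and the summary by treatment group are both in the protocol, and a later SAP cannot reliably identify Holter-only events if the source of detection was not captured at entry. Excluding substudy patients is a weaker substitute, because it removes a selected low-risk group from the plitidepsin arms only. The last objection is met by keeping every event in the main tables.

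**Conclusion.** The point holds as a minor one. Extra cardiac surveillance is confined to the plitidepsin arms, a filtered route leads from Holter to adverse event, and section 8.7 does not separate what that route adds. The comparison is open to detection bias, and its direction is against plitidepsin.

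The size is unknown because no Holter yield is given. Under an assumed extra yield of 2% to 20%, the pooled plitidepsin rate rises by 0.25 to 2.5 percentage points (1 to 10 patients), or by 0.5 to 4.9 points in one dose arm if all 50 were in it. Under the second set of assumptions the ratio to control is 1.00 to 1.49. It would therefore go too far to say that an inert drug would necessarily show a cardiac excess. Nor is the plitidepsin-only inclusion criterion a mistake: the fault lies in how substudy findings flow into the main safety tables.

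**What to change.** 1. Keep all events in the main safety tables.
2. Add an eCRF flag for adverse events first detected only through the substudy Holter or a central ECG alert, completed when the event is entered.
3. State in section 8.7 that the summary by arm of cardiac treatment-emergent events and events of special interest is repeated as a sensitivity analysis without flagged events, and that flagged events are tabulated separately.
4. As a further check, repeat that summary without substudy patients. Label it supportive, because it removes low-risk patients from the plitidepsin arms only.
5. State that the main-study tables of QTcF above 500 msec and change above 60 msec use the scheduled ECGs common to all arms.

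The cost is one eCRF field, a few sentences in section 8.7 and one or two extra tables. No event leaves safety reporting. The flag is assigned by staff who know the arm, which is a further reason to use it for a sensitivity analysis and not to define the main comparison.
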